5.2.7.2 Definitive Contraindications

Should a subject experience 1 or more of the conditions listed below after the first dose of study vaccine, the Investigator will not administer the second dose of vaccine that has been allocated for use in the study (i.e., study vaccine); however, the Investigator may administer a second dose of licensed, non-study influenza vaccine in accordance with standard clinical care.

Definitive contraindications include:

- An anaphylactic or other significant allergic or serious reaction to the previous dose of vaccine.

^a Investigators are highly encouraged to evaluate signs and symptoms to establish and report a diagnosis whenever feasible; reporting only signs and symptoms in lieu of a unifying diagnosis is strongly discouraged

- Receipt of any non-study vaccine (including a non-study dose of 2016–2017 influenza vaccine), immune globulins, blood, or blood-derived products between Visit 1 and Visit 2.
- Bleeding disorder, receipt of anticoagulants, or thrombocytopenia, which may be a contraindication for intramuscular vaccination, at the discretion of the Investigator.
- Development of any condition that in the opinion of the Investigator would pose a health risk to the subject or could interfere with the evaluation of the study vaccine (including GBS, clinically significant developmental delay, neurologic disorder, seizure disorder, human immunodeficiency virus, hepatitis B, or hepatitis C).
- Development of an immunodeficiency; or receipt of immunosuppressive therapy such as anti-cancer chemotherapy or radiation therapy; or receipt of long-term systemic corticosteroid therapy (prednisone or equivalent for more than 2 consecutive weeks).
- Adverse events that are considered a contraindication for further participation in the trial.
- Poor or non-compliance by the subject. In cases where a subject is outside the recommended visit schedule, the subject may be continued in the study as a protocol violator and will be analyzed accordingly.

Subjects will not be withdrawn due to a definitive contraindication but will be followed up for safety and possibly immunogenicity assessment.

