9.3.1.2 Safety Endpoints

The observational endpoints for the evaluation of safety are:

- 1) Occurrence, nature (Medical Dictionary for Regulatory Activities [MedDRA] preferred term), duration, intensity, and relationship to vaccination of any unsolicited systemic AEs reported in the 20 minutes after each vaccination.
- 2) Occurrence, time to onset, number of days of occurrence, intensity, action taken, and whether the reaction led to early termination from the study, of solicited injection site reactions (prelisted in the subject's diary card and eCRF) occurring between Day 0 and Day 7 after each vaccination.
- 3) Occurrence, time to onset, number of days of occurrence, intensity, action taken, and whether the reaction led to early termination from the study, of solicited systemic reactions (prelisted in the subject's diary card and eCRF) occurring between Day 0 and Day 7 after each vaccination.
- 4) Occurrence, nature (MedDRA preferred term), time to onset, duration, intensity, action taken, relationship to vaccination (for systemic AEs only), and whether the event led to early

^a All injection site AEs are considered to be related to vaccination; therefore, all *injection site* AEs are *injection site reactions*.

termination from the study, of unsolicited AEs between Visit 1 and Visit 2 for subjects receiving 1 dose or between Visit 1 and Visit 3 for subjects receiving 2 doses.

5) Occurrence, nature (MedDRA preferred term), time to onset, seriousness criteria, relationship to vaccination, outcome, and whether the SAE led to early termination from the study, of SAEs between Visit 1 and Visit 2 for subjects receiving 1 dose or between Visit 1 and Visit 3 for subjects receiving 2 doses.

Adverse events of special interest will be captured as SAEs. These include new onset of GBS, encephalitis/myelitis (including transverse myelitis), neuritis (including Bell's palsy, optic neuritis, and brachial neuritis), thrombocytopenia, vasculitis, convulsions (including febrile convulsions), and anaphylaxis or other hypersensitivity/allergic reactions between Visit 1 and Visit 2 for subjects receiving 1 dose, or between Visit 1 and Visit 3 for subjects receiving 2 doses.

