9.3.1.3.4 Serious Adverse Events

Information on SAEs will be collected and assessed throughout the trial, from Visit 1 until Visit 2 (or from Visit 1 to Visit 3 for those subjects receiving 2 doses).

Any SAE occurring at any time during the trial will be reported by the Investigator through the EDC system and according to the completion guidelines provided by the Sponsor. All information concerning the SAE is to be reported, either as part of the initial reporting or during follow-up reporting if relevant information became available later (e.g., outcome, medical history, results of investigations, copy of hospitalization reports). The Investigator will assess the causal relationship between the SAE and the investigational product as either “Not related” or “Related”, as described in [Section 9.3.1.3.6](#).

See [Section 10](#) for further details on SAE reporting.

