### 3.2 Trial Plan

Using a pre-programmed interactive response technology (IRT) system, subjects will be randomly assigned in a 1:1 ratio to either 1 of the following groups:

- Group 1: 0.25 mL of Fluzone Quadrivalent vaccine (approximately 1095 subjects)
- Group 2: 0.5 mL of Fluzone Quadrivalent vaccine (approximately 1095 subjects)

Enrollment will be stratified by age at each site so that approximately 50% of subjects at each site will be 6 to < 24 months of age and approximately 50% of subjects at each site will be 24 to < 36 months of age. If necessary to achieve 50% overall enrollment of subjects 6 to < 24 months of age, individual sites may be permitted to deviate from this ratio.

All subjects will receive 1 intramuscular dose of Fluzone Quadrivalent vaccine (0.25 mL [Group 1] or 0.5 mL [Group 2]) during Visit 1. For subjects for whom 2 doses of influenza vaccine are recommended per ACIP guidance, a second dose of Fluzone Quadrivalent vaccine (same 0.25-mL or 0.5-mL dose as administered at Visit 1) will be administered during Visit 2 (28 [window, 28–35] days after Visit 1).

Blood specimens will be obtained from a planned subset of approximately 1600 subjects randomly selected by an IRT system (half in Group 1 and half in Group 2) prior to the first vaccination and 28 (window, 28–35) days following the final vaccination (Visit 2 for subjects receiving 1 dose; Visit 3 for subjects receiving 2 doses) and assayed for immunogenicity.

Solicited AE information will be collected for 7 days after each vaccination. Unsolicited AE information and serious adverse event (SAE) information will be collected from Visit 1 to Visit 2 for subjects receiving 1 dose or from Visit 1 to Visit 3 for subjects receiving 2 doses.

Note: Any SAE that occurs after a subject has completed the study but that is likely to be related to the product is to also be reported to the Sponsor.

**Table 3.1: Study Procedures - Trial Flow Chart for Subjects 6 to < 36 Months of Age: 2 or 3 Visits, 1 or 2 Vaccinations, 2 Groups**

Visit Number	All Subjects		Subjects Receiving 1 Dose of Influenza Vaccine	Subjects Receiving 2 Doses of Influenza Vaccine		
	Visit 1	Telephone Contact	Visit 2	Visit 2	Telephone Contact	Visit 3
Trial Timelines	Day 0	Visit 1 + 8 days	Visit 1 + 28 days	Visit 1 + 28 days	Visit 2 + 8 days	Visit 2 + 28 days
Time Windows	--	+ 8 to 10 days	+ 28 to 35 days	+ 28 to 35 days	+ 8 to 10 days	+ 28 to 35 days

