**4.3.1.2 Safety Endpoints**

The observational endpoints for the evaluation of safety are:

- 1) Occurrence, nature (Medical Dictionary for Regulatory Activities [MedDRA] preferred term [PT]), duration, intensity, and relationship to vaccination of any unsolicited systemic AEs reported in the 20 minutes after each vaccination.
- 2) Occurrence, time to onset, number of days of occurrence, intensity, action taken, and whether the reaction led to early termination from the study, of solicited injection site reactions (prelisted in the subject's diary card and eCRF) occurring between Day 0 and Day 7 after each vaccination.
- 3) Occurrence, time to onset, number of days of occurrence, intensity, action taken, and whether the reaction led to early termination from the study, of solicited systemic reactions (prelisted in the subject's diary card and eCRF) occurring between Day 0 and Day 7 after each vaccination.
- 4) Occurrence, nature (MedDRA PT), time to onset, duration, intensity, action taken, relationship to vaccination (for systemic AEs only), and whether the event led to early termination from the study, of unsolicited AEs between Visit 1 and Visit 2 for subjects receiving 1 dose or between Visit 1 and Visit 3 for subjects receiving 2 doses.
- 5) Occurrence, nature (MedDRA PT), time to onset, seriousness criteria, relationship to vaccination, outcome, and whether the SAE led to early termination from the study, of SAEs between Visit 1 and Visit 2 for subjects receiving 1 dose or between Visit 1 and Visit 3 for subjects receiving 2 doses.

---

a All injection site AEs are considered to be related to vaccination; therefore, all *injection site* AEs are *injection site reactions*.

Adverse events of special interest will be captured as SAEs. These include new onset of GBS, encephalitis/myelitis (including transverse myelitis), neuritis (including Bell's palsy, optic neuritis, and brachial neuritis), thrombocytopenia, vasculitis, convulsions (including febrile convulsions), and anaphylaxis or other hypersensitivity/allergic reactions between Visit 1 and Visit 2 for subjects receiving 1 dose, or between Visit 1 and Visit 3 for subjects receiving 2 doses.

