### 5.1.3.1 Safety Analysis

The safety analysis will report the occurrence of solicited reactions and the incidence of unsolicited AEs between Visit 1 and Visit 2 (or between Visit 1 and Visit 3 for those subjects receiving 2 doses).

To avoid any under-estimation of the incidences, the number of subjects with documented safety will be used as denominator for the frequencies.

- For solicited reactions, the denominator will be the total number of subjects who have non-missing data for the endpoint considered
- For unsolicited AEs, the denominator will be the total number of subjects who were vaccinated at the dose analyzed.

The safety tables will be produced using a subject approach, i.e., number of subjects who experienced at least 1 safety event during a considered period.

The 2-sided 95% CIs for the percentages will be calculated using the exact binomial method (Clopper-Pearson method).

Additional safety tables, which will be based on analyses that exclude safety data from Site 009, will be presented in the CSR appendices. Specifically, these tables will be those that provide overall safety overviews/summaries and those that describe solicited reactions after any vaccination by maximum intensity.

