### ***Serious Adverse Events***

The number and percentage of subjects with SAEs after vaccination within 28 days after each vaccination in each treatment group will be calculated by outcome, seriousness, and relationship to vaccination.

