## 5.3 Handling of Missing Data and Outliers

### 5.3.1 Safety

No replacement of missing data will be done. All subjects with safety data and all safety data recorded in the eCRFs will be included in the safety analyses. No search for outliers will be performed.

In all subject listings, partial and missing data will be clearly indicated as missing.

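### Read literally, the SAP's SAE summary by outcome, seriousness and relationship stops 28 days after each vaccination, while the SAE endpoint it reports runs to the visit at Day 28 to 35

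*SAP*

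**What the plan says.** The analysis text in SAP 5.1.3.1, Serious Adverse Events, gives this rule for its subject counts: "SAEs after vaccination within 28 days after each vaccination in each treatment group will be calculated by outcome, seriousness, and relationship to vaccination".

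The endpoint is defined by visits. Item 5 of SAP 4.3.1.2 lists, among other attributes, "seriousness criteria, relationship to vaccination, outcome, and whether the SAE led to early termination from the study, of SAEs between Visit 1 and Visit 2" in one-dose subjects, and extends the period to Visit 3 for two-dose subjects. Protocol 9.3.1.2 has the same item. It adds, as the SAP does, that "Adverse events of special interest will be captured as SAEs", over the same visit-based period.

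Collection follows the endpoint. Protocol 9.3.1.3.4 says "Information on SAEs will be collected and assessed throughout the trial, from Visit 1 until Visit 2", or until Visit 3 after two doses.

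The closing visit is not fixed at Day 28. SAP 3.2 times the last blood draw, which is taken at that visit, at "28 (window, 28–35) days following the final vaccination". Table 3.1 gives Visit 2 and Visit 3 the same window of 28 to 35 days after the preceding visit. A visit can be later still. Protocol 5.2.7.2 says: "In cases where a subject is outside the recommended visit schedule, the subject may be continued in the study as a protocol violator".

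The opening of SAP 5.1.3.1 uses the visit-based period for its other long-term summary, namely "the incidence of unsolicited AEs between Visit 1 and Visit 2 (or between Visit 1 and Visit 3 for those subjects receiving 2 doses"). The paragraphs on unsolicited injection site reactions and unsolicited systemic events do the same.

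**The concern.** The SAE paragraph breaks events down by outcome, seriousness and relationship. Those are attributes that endpoint item 5 names, so this is the analysis of that endpoint, yet it states a shorter period. A programmer who follows the sentence would filter on onset at or before Day 28. An SAE on Day 31, before a visit on Day 34, would then be collected and would belong to the endpoint, but would be absent from the table.

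In a two-dose subject whose second dose comes late in the window, an SAE that starts after Day 28 but before Dose 2 falls in neither 28-day period.

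At stake is whether the SAE counts in the study report reconcile with the endpoint and with the unsolicited-AE tables in the same section. The trial is meant to support a change to the Prescribing Information in young children (protocol 1.4), so a mismatch in serious events is worth avoiding, even a small one.

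**Working it through.** The plan gives no figure to reproduce on this point. The check compares the stated periods and then counts days.

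**Step 1. The stated periods**

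| Place | Period |
|---|---|
| SAP 4.3.1.2 and protocol 9.3.1.2, SAE endpoint and events of special interest | Visit 1 to Visit 2 (one dose) or Visit 3 (two doses) |
| Protocol 9.3.1.3.4 and SAP 3.2, SAE collection | Same |
| SAP 5.1.3.1, unsolicited AEs | Same |
| SAP 4.4.1.3, SAE derivation rules | Dose assigned by visit number or, failing that, start date; no 28-day limit |
| SAP 5.1.3.1, Serious Adverse Events | 28 days after each vaccination |

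Only the last row differs. SAP 5.7 declares no change to planned analyses that would explain it.

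**Step 2. Days outside the table**

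Inputs: the visit is 28 to 35 days after the preceding dose (SAP 3.2 and Table 3.1), and the literal limit is 28 days (SAP 5.1.3.1). Onset is the start date minus the date of the previous vaccination (SAP 4.4.1.3.2, which refers to 4.4.1.2.3).

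Uncovered share = (days from dose to visit − 28) / (days from dose to visit), with numerator and denominator each summed over the dosing intervals.

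- One dose, visit at Day 28: 0/28 = 0%.
- One dose, visit at Day 35: 7/35 = 20%.
- Two doses, intervals 28 + 28: 0/56 = 0%.
- Two doses, one interval of 28 and one of 35: 7/63 = 11.1%.
- Two doses, intervals 35 + 35: 14/70 = 20%.

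These are elapsed days. Counting calendar days from Day 0 to Day 35 instead gives 7/36 = 19.4% for one dose, so the convention hardly matters. A subject continued off schedule with a visit after Day 35 would exceed 20%.

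**Step 3. What this means in events**

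If SAE onsets were spread evenly over follow-up (an assumption), 10 × 0% = 0 to 10 × 20% = 2 of every 10 SAEs would fall outside the table. The documents give no SAE rate, so no number of subjects can be stated.

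Even onset probably overstates the loss of vaccine-related events. Protocol 1.3.2 places the febrile seizure risk on the day of vaccination and the day after, and the peak of Guillain-Barré cases at two weeks.

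**Step 4. Where a late SAE would still be seen**

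Under SAP 4.3.1.1, non-serious unsolicited AEs are the unsolicited AEs that remain once SAEs are taken out, so SAEs are within unsolicited AEs. Those are summarised over the visit-based period in the safety overview, by system organ class, preferred term and relationship. Outcome and seriousness are not among the listed breakdowns. In the visible text the SAE paragraph is the only summary that gives them.

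**The case against.** The strongest reply is that 28 days is shorthand for the visit. SAP 4.2.1 states both secondary endpoints at 28 days without the window, while SAP 5.1.2.2 writes the window out. The SAE derivation rules contain no 28-day filter, which fits shorthand too. The 7-day wording for solicited reactions in SAP 5.1.3.1 does not decide the matter: it is a real limit, but it is also an informal restatement of a period fixed elsewhere.

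This reading is possible and cannot be excluded. However, no passage states it, the next subsection (SAP 5.1.3.2) writes out the 28 to 35 day window, and the SAE sentence is phrased as a limit and not as a time point.

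The second reply also has force. Protocol 12.1.3.1 is redacted and the table shells are in a separate file (SAP 6), so a full-period SAE table by outcome and seriousness may already exist.

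A reader might infer two stronger points, and the documents support neither.

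- That the paragraph also contradicts SAP 5.3.1, which says "All subjects with safety data and all safety data recorded in the eCRFs will be included in the safety analyses". That sentence belongs to the rules on missing data and outliers. It does not require every table to hold every event, and the 20-minute and Day 0 to 7 tables legitimately use shorter periods. It is background only.
- That late SAEs vanish from the report. As shown above, they should remain in the visit-based unsolicited-AE summaries with their nature and relationship.

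**Conclusion.** The inconsistency is real but narrow. As written, one descriptive SAE summary covers a shorter period than the endpoint it reports. The difference is 0 to 7 days per dosing interval on schedule: 0% to 20% of follow-up for one-dose subjects and, with both intervals at Day 35, up to 14 of 70 days for two-dose subjects. The 20% is a ceiling, because it needs every visit to fall on Day 35.

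The conclusion rests on the literal reading and on the visible text. What is affected is the breakdown by outcome and seriousness for SAEs with late onset.

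It would be wrong to infer a biased comparison or a safety-reporting gap. The wording is identical for both groups, the primary fever analysis uses Day 0 to Day 7, and SAE reporting to the sponsor under protocol 10 does not depend on this table. The point is worth correcting because the change is so cheap. Confidence is medium, given the possible shorthand and the unseen shells.

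**What to change.** In SAP 5.1.3.1, Serious Adverse Events:

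- State the overall summary period as Visit 1 to Visit 2 for one-dose subjects and Visit 1 to Visit 3 for two-dose subjects, matching SAP 4.3.1.2 and the unsolicited-AE paragraphs of 5.1.3.1.
- Keep the breakdown by vaccination, which the SAP's dose-assignment rules for SAEs (4.4.1.3.1) and the protocol's per-dose safety analysis (12.2.1) support. Let each interval run from the vaccination to the next scheduled visit (Dose 1 to Visit 2, Dose 2 to Visit 3) instead of ending at Day 28.
- Check that the filter in the table shells matches.

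If 28 days was meant as shorthand for the visit, the same edit makes that explicit. A strict 28-day table can stay as an addition.

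The cost is a sentence in the SAP and one check of a table filter. The downside is that reported SAE counts may be slightly higher.

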#### **5.1.3.2 Immunogenicity Analysis**

The following immunogenicity parameters will be calculated for each influenza strain with 95% CIs of point estimates calculated using the exact binomial distribution (Clopper-Pearson method) for proportions and using normal approximation for GMTs:

- Geometric mean HAI assay titers at pre-vaccination (Day 0) and at 28 (window, 28–35) days after the final vaccination.
- Geometric means of the individual titer ratios of post-final vaccination/pre-vaccination.
- Seroprotection rates: The percentages of subjects with a titer  $\geq 40$  (1/dil) at pre-vaccination and at 28 (window, 28–35) days after the final vaccination.
- Seroconversion rates: The percentages of subjects with either a pre-vaccination titer  $< 10$  (1/dil) and a post-vaccination titer  $\geq 40$  (1/dil), or a pre-vaccination titer  $\geq 10$  (1/dil) and a  $\geq 4$ -fold increase in post-vaccination titer at 28 (window, 28–35) days after the final vaccination.

## **5.2 Analysis Sets**

Three analysis sets will be used: The SafAS, the FAS, and the PPAS.

### 5.2.1 Safety Analysis Set

The SafAS is defined as those subjects who have received study vaccine.

### 5.2.2 Full Analysis Set

### 5.2.3 Per-Protocol Analysis Set

- Subject did not meet all protocol-specified inclusion criteria or met at least 1 of the protocol-specified exclusion criteria
- Subject did not complete the vaccination schedule as per protocol
- Subject received a vaccine dose other than the one that he/she was randomly assigned to receive
- Preparation and/or administration of vaccine was not done as per protocol
- For subjects receiving 2 doses of vaccine, subject did not receive the second dose within the proper time window (28–35 days after the first vaccination)
- Subject did not provide a post-dose serology sample in the proper time window (28–35 days) after the final vaccination or a post-dose serology sample was not drawn
- Subject received a protocol-prohibited therapy/medication/vaccine that might impact antibody response to the study vaccine
- Subject's post-vaccination serology sample did not produce a valid HAI test result for any strain
- Any other deviation identified during conduct of the study conduct and judged by the clinical team during data review as having a potential impact on the assessment of immunogenicity
- Other protocol deviations that will result in the exclusion of a subject from the per-protocol analysis set include:
  - Re-randomization of a subject
  - Inclusion in the immunogenicity subset after not being assigned to the subset originally
  - Receipt of study vaccine not corresponding to the medication ID assigned to the subject

## 5.2.4 Populations Used in Analyses

Baseline and demographic analyses will be performed on SafAS, FAS and PPAS.

The safety analyses will be performed on the SafAS.

The analysis of the primary endpoint, rate of fever (temperature  $\geq 100.4^{\circ}\text{F}$  [ $38.0^{\circ}\text{C}$ ]), is based on fever caused by either vaccination (Dose 1 and Dose 2 combined).

All subjects will have their safety analyzed after any dose according to the vaccine they actually received at the first dose. Safety data recorded for a vaccine received out of the protocol design will be excluded from the analysis (and listed separately).

The immunogenicity analyses will be performed on both the FAS and PPAS. The PPAS will be the primary analysis set for assessing non-inferiority by immunogenicity.

